Laboratory space: Laboratory space in Williams Hall contains filtration devices to remove any secondhand smoke or aerosol (from cigarettes or ENDS). In consultation with [name] at Virginia Commonwealth University and [name], Executive Director of Facilities at EVMS, approximately \$50,000 was spent designing and equipping these rooms. This laboratory was designed for smoking research and includes a ventilation system so that others are not exposed to second-hand smoke unduly.

Sample size: A total of 30 participants are planned to allow for statistical power to examine differences (Within-Subjects) in the physiological and subjective effects of the products. Using a Repeated Measures Within-Subjects design, this will allow for detection of a large effect size (Cohen, 1992; Faul et al., 2009). We may consent up to 75 participants in order to obtain 30 participants who complete the entire study.

Recruitment: We will recruit current cigarette smokers using a recruitment database submitted separately (PR-2871-EVMS). Potential participants will find this recruitment database via advertising on Craigslist, newspapers, internet forums, flyers in the local area, and local clinics. There is a flyer specifically for this study that will direct individuals to participate in the registry online questionnaire. Screening data will be obtained from this online questionnaire. See separate protocol submitted. Screening data will be compared against the inclusion and exclusion criteria listed below to determine if participant is eligible for this study. Eligible participants will be contacted to provide more information about the study. Participants will be told they can smoke as normal for their first visit, but must abstain for 12 hours (typically overnight) before the 3 other visits. Those who meet screening criteria and are still interested in the study will be scheduled to come in for laboratory visits.

Inclusion Criteria: All participants must be healthy (determined by self-report), between the ages of 18-55, willing to provide informed consent, and willing to attend the EVMS lab 4 times and abstain from smoking for 12 hours (typically overnight) for 3 of these visits. Participants must smoke at least 10 cigarettes per day (i.e., be regular cigarette smokers). Self-report of smoking will be bioverified on the initial screening visit.

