Initial laboratory screening visit: Potential participants will be informed prior to this session to provide a list of current prescription medications or bring in their medication bottles in with them to confirm any medications listed on the screening survey. When participants arrive, air filters will be on in the laboratory space in order to encourage familiarity with the noise during laboratory sessions. Potential participants will be provided with a copy of the informed consent document. (See attached.) Research Assistants will review the informed consent document with the potential participant and answer any questions. If still interested, the form will be signed and a copy provided. Next, participants will breathe into a Carbon Monoxide (CO) monitor. (Cigarette smoking involves the inhalation of Carbon Monoxide.) In addition, participants will provide a saliva sample to test for cotinine, a metabolite of nicotine. If participants do not have a CO level of at least 15 ppm and a cotinine test strip level of at least 3 (indicating 100-200 ng/ml cotinine), then they will not be allowed to continue with the study. These results would indicate that they are not regular cigarette smokers. Female participants will also provide a urine sample using the nearby restroom. A pregnancy test strip will be used. If the test does indicate pregnancy, the result will be discussed with the participant and she will be urged to seek prenatal medical care. Information will be provided about where to receive such care (either with their regular physician or at a free clinic). Otherwise, staff will next assess heartrate and blood pressure using an arm blood pressure cuff and a pulse oximotor. Participants will be deemed ineligible at screening if their resting heart rate (HR) exceeds 110 beats per minute (bpm), systolic blood pressure (BP) exceeds 140 mm Hg, or diastolic BP exceeds 100 mm Hg. If they do demonstrate eligibility (regular cigarette smoker, not pregnant, acceptable vital signs), they will complete a W9 to facilitate payment processing and complete baseline questionnaires (DemographicPersonalHealthInfo, PennState, Fagerstrom, BaselineExpectancies) on the REDCap system. (See attached document.) Finally, following completion of the baseline questionnaires, the Research Assistant will review with the participant the next 3 scheduled visits and emphasize the need to abstain from smoking and nicotine products for 12 hours (typically overnight) and pass testing before their next visit.

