
Smoking/Vaping" Lab Sessions: The sessions will occur no more than 2 days per week and will be separated by at least 48 hours. The approximate total time that participants will be in the laboratory is 12.5 hours (30 minutes for screening and 12 hours for 3 4-hour long sessions). This does not include the 12 hours before each session that we ask participants to abstain from smoking.

Note: Most questionnaires are completed via computer in the laboratory. The only exception for subjects is the glms, administered via pen & paper. EnrollmentInformation, SessionInformationSheet, BiochemicalTestResults, and the SaltStudySessionSheet are completed by Research Staff.

The session will begin with the participants' self-report of their last cigarette, CO expired air testing, and cotinine saliva testing. If the last cigarette smoked was within 12 hours or CO is above 10 ppm, the participant will be told they need to reschedule for another time and must abstain for 12 hours before the next visit. If there are 2 consecutive sessions indicating non-compliance, the participant will be disqualified from the study and paid as outlined in the compensation section. If participant's tobacco abstinence is bioverified, they will begin a 1-hour waiting period to ensure nicotine abstinence. Nicotine abstinence (e.g., ENDS, NRT) unfortunately cannot be bioverified quickly. Blood analyses at VCU CSTP have indicated high rates of lack of compliance, but much better data in protocols that involve a 1-hour waiting period in the lab. After this waiting period, the participant will continue on with physiological equipment attachment and catheter insertion. Physiological equipment (Criticare 506DNP3R, includes blood pressure cuff and SpOv2 sensor) will continuously measure BP/HR by trained Research Assistants or the study PI.

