Risks to subjects: The protocol uses established methods and procedures and involves only minimal risks to participants. Twelve hours of tobacco abstinence may cause mild discomfort and nicotine abstinence symptoms, but is not medically dangerous. Symptoms may include: irritability, anxiety and restlessness, excessive hunger, difficulty concentrating, and sleep disturbance. The risks of using ENDS/tobacco products/nicotine are routine for the target population. As participation involves consumption of widely available, legal, over-the-counter products that can reduce the harm associated with their current nicotine use, they do not involve significant risks to participants. Risks of nicotine use by nicotine-naïve individuals include sweating, lightheadedness, dizziness, nausea, vomiting, and nervousness. These effects are unlikely in individuals who use nicotine-containing products regularly. In addition, some people who use e-cigarettes have reported experiencing seizures. Some of these individuals reported a prior history of seizures or using other substances at the same time as their e-cigarette. In many cases e-cigarette use has led to respiratory illnesses such as difficulties breathing, shortness of breath and/or chest pain before hospitalization. In some cases, e-cigarette use has led to death, and the Centers for Disease Control and Prevention has advised people to stop vaping. In some cases symptoms of mild to moderate gastrointestinal illness such as vomiting, diarrhea, or fevers or fatigue have been reported.

It is unlikely that the questionnaires will pose any potential risk or discomfort (no sensitive questions are asked). Sessions are relatively short and can be completed at the participants' own pace. With any research, there is always risk of loss of confidentiality. However, the risk is very low for the reasons listed below.

Steps taken to minimize risks / harms: Participant safety and rights will be protected by highly trained staff. Participants will be informed of the potential symptoms of nicotine abstinence/withdrawal and will be told they are free to leave the study at any time.

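### Pregnancy is ruled out once, by a urine strip at screening, and is never rechecked before the three product sessions

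*Combined protocol and SAP*

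**What the plan says.** Under *Initial laboratory screening visit*, women give a urine sample that is tested with a pregnancy strip. Participants continue to the baseline questionnaires "If they do demonstrate eligibility (regular cigarette smoker, not pregnant, acceptable vital signs" all being satisfied. For a positive result, "If the test does indicate pregnancy, the result will be discussed with the participant and she will be urged to seek prenatal medical care", and she is told where to obtain it.

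Under *Smoking/Vaping Lab Sessions*, each product session opens with "self-report of their last cigarette, CO expired air testing, and cotinine saliva testing". The session timeline adds a one-hour wait, monitoring equipment, a catheter, product use, CO readings and questionnaires. No step is a pregnancy test. Timing is governed by "The sessions will occur no more than 2 days per week and will be separated by at least 48 hours". After a failed abstinence check "the participant will be told they need to reschedule for another time", and two consecutive failures disqualify.

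*Inclusion Criteria* admits people "between the ages of 18-55". Neither it nor *Exclusion criteria* mentions pregnancy or contraception. Under *Steps taken to minimize risks / harms*, respiratory questions are asked at screening and again before every session. *Risks to subjects* warns: "In some cases, e-cigarette use has led to death, and the Centers for Disease Control and Prevention has advised people to stop vaping". On numbers, *Sample size* says "We may consent up to 75 participants in order to obtain 30 participants who complete the entire study".

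**The concern.** The protocol has decided that pregnant smokers should not take part, but it enforces that decision only on the screening day. Its three named entry conditions are treated differently afterwards. Vital signs are monitored during sessions, and smoking biomarkers are measured again, although there to confirm abstinence. Pregnancy status is not revisited.

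The spacing rule is a minimum. The text sets no maximum time from screening to any session, so the negative result has no expiry date.

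At stake is the safety of a participant who becomes pregnant between screening and a session. Two of the three products are ENDS, each with a 90-minute ad lib period, and enrolment requires no ENDS use in the previous 30 days, so this is not her current routine exposure. She would also miss the discussion and referral that the same result would have triggered at screening.

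**Working it through.** **Reading the text.** The plan gives no figure to reproduce. Three places might have contained a repeat check:

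- *Screening visit, closing instruction.* Participants are told they must pass testing before the next visit. This completes the instruction to abstain, and the session section specifies that testing as last cigarette, CO and cotinine.
- *Session procedures and timeline.* No urine sample or pregnancy test appears.
- *Pre-session health questions.* These are respiratory only.

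**Earliest session days**, with screening on day 0 and session 1 possible on day 1 after 12 hours' abstinence:

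- Two days per calendar week: days 1, 3, 5 (for example screening Wednesday, sessions Thursday, Saturday, Monday).
- Two days per rolling 7 days: days 1, 3, 8.
- Weekly sessions (my assumption): days 7, 14, 21.

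**Expected number newly positive.** Formula: women × monthly rate × days ÷ 30. Assumptions not in the documents: 15 women among 30 completers; 0.5% to 3% becoming strip-positive per 30 days, averaged over all enrolled women including those unable to conceive.

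| Days since last negative | Low (rate 0.005) | High (rate 0.03) |
|---|---|---|
| 1 | 15 × 0.005 × 1/30 = 0.0025 | 15 × 0.03 × 1/30 = 0.015 |
| 3 | 0.0075 | 0.045 |
| 5 | 0.0125 | 0.075 |
| 7 | 0.0175 | 0.105 |
| 8 | 0.020 | 0.120 |
| 21 | 15 × 0.005 × 21/30 = 0.0525 | 15 × 0.03 × 21/30 = 0.315 |

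With 10 women the range is 0.013–0.08 at day 8 and 0.035–0.21 at day 21. With 20 women it is 0.027–0.16 and 0.07–0.42. The day-7 row is the ceiling at any session under a 7-day limit, however long the delay.

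**Strips needed.**

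- Every session: 15 × 3 = 45. Upper limit if all 75 consented, half were women and all started three sessions: 75 × 0.5 × 3 = 112.5.
- Only when the last negative is over 7 days old: none on days 1, 3, 5; one per woman on days 1, 3, 8 (at day 8); one per woman on days 7, 14, 21 (at day 14). For 15 women that is 0, 15 and 15.

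**False positives**, assuming 0.1–1% per strip:

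- 45 strips: 45 × 0.001 = 0.045 to 45 × 0.01 = 0.45.
- 15 strips: 0.015 to 0.15.
- Two false positives running, if independent, over 45 strips: 45 × 0.001² = 0.000045 to 45 × 0.01² = 0.0045. If errors are correlated, the figure lies between this and the single-strip range.

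**The case against.** The best case for leaving the plan alone has five parts.

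- **No rule is broken.** Non-pregnancy is stated as a condition at entry, and one test at entry to a short laboratory study is a legitimate choice. That is true; this is a design choice that can be improved, not a contradiction.
- **Other material may cover it.** Staff forms such as the biochemical results sheet, the attachments and the consent pages are not available here. A repeat strip in any of them would meet the point, so the conclusion is limited to the text at hand.
- **Staff already question participants before each session.** A known pregnancy might surface then. But the questions are respiratory, and an unrecognised pregnancy would not emerge.
- **The harm is thin.** Participants already smoke at least 10 cigarettes a day, one product is their own brand, and the protocol expects nicotine intake at or below their usual level. The e-cigarette harms it lists are not specific to pregnancy. This stands and keeps the priority low, though it does not make ENDS use routine for people with no use in the past 30 days.
- **The numbers are assumed and the remedy has errors of its own.** All the rates come from outside the documents, and the 7-day limit is a judgement. At 5–8 days false positives can equal or exceed true ones, so a confirmatory strip is needed. Delay is also partly bounded, since visits are already booked at screening and two consecutive abstinence failures disqualify. Other delays have no cap.

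**Conclusion.** The concern holds on the available text: the only pregnancy safeguard is one strip at screening, with no repeat and no limit on the age of the result. The expected number of affected women among completers is well below one under every schedule examined. The size depends on the assumed number of women, the conversion rate and the session dates; it grows in proportion to delay. It is a low-priority participant-safety improvement, worth making because it is cheap. Sample size, power and analysis are unaffected.

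**What to change.** In the session procedures, add a urine pregnancy strip for female participants to the checks before each product session, or at minimum whenever the last negative result is more than 7 days old. If the strip is positive, give no product that day and repeat the test on a fresh sample. If confirmed, end participation and follow the screening-visit discussion and referral. If not confirmed, reschedule the session.

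This takes one or two sentences and uses a test already in the protocol. Women would have to give urine at sessions. With the confirmatory strip, a false positive should usually cost a postponed session rather than a completer. If an existing form already requires a repeat strip, stating so in the session section is enough.

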Exclusion criteria: Individuals will be excluded based on a self-reported history of (1) unstable or significant current medical condition (recent heart attack or other heart conditions including high blood pressure); (2) severe immune system disorders (uncontrolled HIV/AIDS,

unstable multiple sclerosis symptoms), (3) respiratory diseases (exacerbations of asthma or COPD, require oxygen, require oral prednisone), kidney (dialysis) or liver diseases (cirrhosis) or any medical disorder/medication that may affect participant safety, study outcomes, or biomarker data will be excluded. Individuals who report more than 25 days of alcohol use in the past 30 days or more than 15 days of marijuana use in the past 30 days will be excluded. Individuals with past month use of cocaine, opioids, benzodiazepines, and methamphetamine will be excluded. Participants with current, diagnosed psychiatric conditions will also be excluded. Participants will be excluded for any use of an ENDS product in the past 30 days, or any report of daily use of ENDS for a week or more. Regular use of ENDS is excluded as we are interested in understanding the effect of these liquids on smokers who are relatively naïve to ENDS use so that prior experience does not obscure laboratory experience of use.

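### Participants are told to go 12 hours without any nicotine product, but the session-start question and reschedule rule cover only cigarettes and CO

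*Combined protocol and SAP*

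**What the plan says.** The combined protocol and SAP describes the abstinence requirement in several places, with different scope.

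- **Initial laboratory screening visit.** Staff are to "emphasize the need to abstain from smoking and nicotine products for 12 hours (typically overnight) and pass testing before their next visit". This covers nicotine products as well as smoking.
- **Inclusion Criteria.** Participants must be willing to "abstain from smoking for 12 hours (typically overnight) for 3 of these visits". This covers smoking only. Recruitment does not name nicotine products either.
- **Compensation.** The 12 hours are described as abstinence from tobacco products.
- **Smoking/Vaping Lab Sessions.** "The session will begin with the participants' self-report of their last cigarette, CO expired air testing, and cotinine saliva testing". The action rule follows: "If the last cigarette smoked was within 12 hours or CO is above 10 ppm, the participant will be told they need to reschedule". Then: "If there are 2 consecutive sessions indicating non-compliance, the participant will be disqualified from the study". No cut-off or action is attached to the session-start cotinine result.
- **The same paragraph** acknowledges a limit: "Nicotine abstinence (e.g., ENDS, NRT) unfortunately cannot be bioverified quickly". It responds with a 1-hour wait in the laboratory. It reports high non-compliance in blood analyses at the collaborating centre, and considerably better data where such a wait was used. No rates are given.
- **Exclusion criteria.** "Participants will be excluded for any use of an ENDS product in the past 30 days", and also for any past spell of daily ENDS use lasting a week or more.
- **Data Analysis.** Plasma nicotine and heart rate are analysed over three products and four time points, the first before product use. The planned contrasts are paired t-tests of means at the two post-use time points.

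**The concern.** The instruction and the rule that enforces it do not match. A participant who uses an ENDS or NRT within the 12 hours has broken the instruction given at screening but meets neither reschedule trigger. CO will not show it: the protocol treats CO as a marker of cigarette smoking and says that ENDS and NRT abstinence has no quick test. The self-report as described asks about cigarettes, so the question that could bring out such use is not named, and an answer volunteered by the participant has no stated consequence.

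At stake is the starting point of a session. Carried-in nicotine would raise pre-use plasma nicotine and could lower pre-use craving and withdrawal, leaving the product less room to act. The planned contrasts compare post-use means with no stated adjustment for the pre-use value, so whatever is carried in passes into the comparison. Use unrelated to the assigned product would mainly add noise to paired differences in a study of 30 completers.

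**Working it through.** The plan states no figure on this point, so there is none to reproduce. The check is mainly a comparison of texts, followed by two illustrations on stated assumptions.

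**1. Instruction against enforcement**

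| Source of nicotine within 12 h | Covered by screening-visit instruction | Asked about at session start (as described) | Triggers reschedule |
|---|---|---|---|
| Cigarette | Yes | Yes | Yes, by self-report or CO |
| ENDS | Yes | Not named | No |
| NRT | Yes | Not named | No |

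Non-compliance for the disqualification rule is not defined anywhere else, so it takes its content from the cigarette and CO rule just before it. The introduction counts ENDS as tobacco products under US law, yet the lab-session text lets CO verify tobacco abstinence. The term therefore does not settle the scope. The respiratory questions repeated before each session (Steps taken to minimize risks / harms) are described as covering symptoms, not product use.

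**2. What the 1-hour wait secures**

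Inputs from the session timeline: a 60-minute wait, then 35 minutes to the first directed puff, so 60 + 35 = 95 minutes. The plasma nicotine half-life is not in the documents; 1, 2 and 3 hours are assumed. The fraction remaining after time t is 2^(−t / half-life).

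| Assumed half-life | Use just before arrival (95 min) | Use 12 h (720 min) earlier |
|---|---|---|
| 1 h | 2^(−95/60) = 0.33 | 2^(−12) = 0.0002 |
| 2 h | 2^(−95/120) = 0.58 | 2^(−6) = 0.016 |
| 3 h | 2^(−95/180) = 0.69 | 2^(−4) = 0.06 |

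Use just before arrival is the worst case. The dose is unspecified, so these are fractions of an unknown amount, not effects on an outcome.

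**3. How many participants could be touched**

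The documents give no rate. Let p be the assumed probability that a session follows ENDS or NRT use within 12 hours, independent across sessions. The chance of at least one affected session in three is 1 − (1 − p)^3. A paired contrast uses two sessions, so the expected number of unaffected pairs among 30 is 30 × (1 − p)^2.

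| p | 1 − (1 − p)^3 | Completers of 30 with at least one affected session | Unaffected pairs per contrast, of 30 |
|---|---|---|---|
| 0.05 | 0.143 | 4.3 | 30 × 0.9025 = 27.1 |
| 0.10 | 0.271 | 8.1 | 30 × 0.81 = 24.3 |
| 0.20 | 0.488 | 14.6 | 30 × 0.64 = 19.2 |
| 0.30 | 0.657 | 19.7 | 30 × 0.49 = 14.7 |

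The range shows sensitivity to p. It does not estimate p.

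**The case against.** The protocol saw this problem. It names ENDS and NRT, says why they cannot be verified quickly, and adopts the wait for an empirical reason. Entry criteria exclude recent ENDS users, and the exclusion of medication that may affect outcomes or biomarkers arguably covers ongoing NRT. Cotinine and pre-use plasma nicotine are measured. The session forms are attachments outside the main text and might ask about other nicotine. Self-report is also a weak instrument here, because disclosure delays a paid session and a second consecutive failure ends participation.

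Much of this stands, and it limits the point. It does not remove it. The lack of a quick test does not explain why self-report is used for cigarettes and not for other nicotine. Whatever the forms ask, the stated rule does not act on the answer.

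Four stronger readings are tempting but not supported:

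- *Non-compliance will be high in this trial.* The sentence reporting high rates goes on to say that the data are much better with the wait, which this trial uses. It does not say which products were involved.
- *Such use would go undetected.* Pre-use plasma nicotine could reveal it. The gap is that no rule uses the result.
- *Participants who vaped will certainly be kept in.* That is what the written rule implies. What staff would do is not known.
- *Taking up vaping between sessions biases the salt-versus-regular contrast.* The trial itself supplies ENDS in two of three sessions, so no one is naive at the second ENDS session by design. Product order follows a Latin square. Bias would require outside uptake to depend on which liquid came first, and nothing in the documents shows that.

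**Conclusion.** The inconsistency is real and should be corrected. The 12-hour instruction covers nicotine products; the session-start question, the reschedule trigger and, by inheritance, the disqualification rule cover only cigarettes and CO. The wait reduces the exposure but directly secures only 1 of the 12 hours.

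The effect on the results cannot be sized from the documents. It depends on an unknown frequency, limited by the entry criteria, and on an unknown amount of nicotine. The half-life figures show only that the wait and the full 12 hours are far apart across an assumed range of 1 to 3 hours. The counts of affected completers assume independent sessions and a rate between 5% and 30%. No bias in a particular direction is claimed for any contrast. The conclusion rests on the wording of the rules and does not depend on these illustrations.

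**What to change.** 1. **Reconcile the wording** in Recruitment, Inclusion Criteria, Initial laboratory screening visit, Smoking/Vaping Lab Sessions and Compensation, so that one scope of abstinence applies throughout.
2. **Session-start self-report.** Ask for the time of last use of any tobacco or nicotine product: cigarette, ENDS, NRT or other.
3. **Reschedule trigger.** Extend it to last use of any tobacco or nicotine product within 12 hours, or CO above 10 ppm. Keep the existing two-consecutive-failure rule and state that it refers to this definition. The 12 hours and the CO limit are the protocol's own.
4. **Sensitivity analysis.** Repeat the planned contrasts without sessions in which pre-use plasma nicotine indicates recent use, against a cut-off fixed before analysis. Report how many sessions are omitted for each product. Also state whether session-start cotinine has any role.
5. **Optional, descriptive only.** Record ENDS use outside the laboratory between sessions. The 30-day exclusion cannot be reapplied literally after the first ENDS session, because the study supplies the product.

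The cost is one broader question at each session, a revised sentence, one extra analysis on data already collected, and a few more rescheduled visits. Self-report will still miss concealed use. The sensitivity analysis will have fewer pairs, and the omitted sessions will not be a random subset, so it supports the main analysis and does not replace it.
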